Results: In participants with at least one post-baseline visit (n=73), a significant group by visit effect for the HRSD was observed (f=2.61, p=0.025). Depression remission rates were greater in the pregnenolone group (61%) compared to the placebo group (37%), as assessed by the IDS-SR (χ 2(1)=3.99, p=.046). Significant baseline to exit changes in pregnenolone, allopregnanolone and pregNANolone levels were observed in the pregnenolone group but not in the placebo group. In the pregnenolone group, baseline to exit change in the HRSA correlated negatively with changes in allopregnanolone (r=-0.43, p=.036) and pregNANolone (r=-0.48, p=.019) levels. Pregnenolone was well tolerated. Side effects and retention were similar in the two groups.

Due to inclusion and exclusion criteria, people with current active AUD were excluded. However, a total of n=5 for pregnenolone and n=8 for placebo with a history of AUD were enrolled. Among these participants, 50% in the placebo group relapsed to alcohol use during the study as compared to only 28% in the pregnenolone group.

Significance: The data, when combined with our prior pilot study, suggest that pregnenolone decreases depressive symptom severity in BPD. Pregnenolone therapy was associated with significant increases in the GABAergic neurosteroids pregNANolone and allopregnanolone that correlated with improvement in anxiety. We have previously reported extraordinarily high rates of anxiety disorders (e.g. 57% generalized anxiety disorder, 54% panic disorder) in BPD and alcohol dependence.¹¹⁰ *Although, few participants had alcohol use disorders, the data suggest lower relapse rate with pregnenolone than with placebo.* Thus, relationships between improvement in anxiety and increases in neurosteroid levels may be clinically important in this dual diagnosis population.

3.3.b. Experimental Study Overview: A 12-week, randomized, double-blind, parallel-group, placebocontrolled adaptive design study of citicoline and pregnenolone is proposed in 199 persons with alcohol use disorder and bipolar I or II disorder or schizoaffective disorder, bipolar type. The primary aim will be to assess change in alcohol use (drinks per drinking day-primary outcome measure) by the Timeline Followback (TLFB) method.^{111, 112} Biomarkers of alcohol use, alcohol craving, mood and cognition will also be assessed. Relationships between neurosteroid and choline levels and the outcome measures will be explored.

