- 1. The trial will be stopped if neither active treatment appears to be effective (both active treatment effect sizes are smaller than a minimum clinically important difference, defined as an effect size of 0.25).
- 2. The trial will continue to Stage 2, if there is evidence (based on precision analysis i.e., a smaller interval width) that at least one treatment from the interim analysis at end of Stage 1 is more effective than placebo. If both treatments appear to be effective in Stage 1 then the trial will continue with three-arms. Findings from the interim analysis may result in change in sample size required for achieving statistical

significance at a desired power. At the end of Stage 2, data collected from both stages will be combined for a final analysis. Depending on the results of the interim analysis, blinded sample size re-estimation may be performed per recommendation from the DSMB.

Stage 2 will be a two-arm (assuming that only one promising treatment is retained) randomized study comparing the selected treatments from Stage 1 versus the placebo. At the end of the Stage 2, the selected treatment will be compared with placebo using the number of drinks per drinking day as the primary outcome measure. At each stage, the primary efficacy analysis will be performed based on the intention-to-treat (ITT) population, defined as all randomized participants who have at least one follow-up evaluation regardless of their compliance with the protocol. In case of substantial numbers of protocol violations, a per-protocol analysis may be done to determine whether they influence the conclusions. At end of Stage 2 (or end of trial), a clinical superiority test may be performed after non-inferiority has been established, without paying any statistical penalty.

Sample size re-estimation: Sample size re-estimation will be performed based on the number of drinks per drinking day as the primary outcome measure. Sample size calculations will be performed as follows:¹³²

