At Stage 1, we will recruit 99 subjects (i.e., 33 subjects per arm) with 1:1:1 treatment allocation ratio, which provides clinically meaningful minimum *effect size of 0.25 between each treatment arm and placebo with* a two-sided test at the 5% level of significance. After review of interim data, an additional 100 subjects at 1:1 ratio will be recruited at Stage 2. If the effect size for *both* medications is at least 0.50 at interim analysis then we will have 81.4% power with 66 participants per arm and the study will continue with three treatment arms. To summarize: 1) If neither treatment has an effect size of at least 0.25 at interim analysis then the trial is discontinued. *This effect size was selected because it is a clinically meaningful value. Naltrexone has an average effect size of approximately 0.15-0.20 in clinical trials for alcohol dependence.*¹³³ *Thus, a useful new treatment for alcohol dependence should at least have a larger effect size than the standard treatment. This effect size of 0.25 is also an effect size at interim analysis that provides a reasonable likelihood of a significant difference from placebo at study completion assuming some increase in effect size as more participants are*

enrolled and the variance of the data decreases. 2) If one treatment has an effect size of at least 0.25 then the trial continues dropping the less effective treatment (two-arm study of one medication vs. placebo). 3) If both treatments have an effect size of at least 0.50 then neither treatment is dropped and the trial continues as a three-arm trial (both medications vs. placebo). This assumes that the DSMB assessment determines that the selected treatment(s) has an adequate safety and tolerability profile to continue the trial. We anticipate that the interim analysis will take place at approximately month 26 of the study. As an incentive to enroll quickly and avoid prolonging the study, we will mandate that an interim analysis take place by month 34 even if fewer than 99 participants have been enrolled. All interim analysis decisions will be made in consultation with the NIAAA program official and DSMB.

Statistical Methods:

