At each stage, a table will show the adverse events (categorized by seriousness, severity, and possible association with study drug) ordered by decreasing frequency for all patients. If appropriate, the incidence rate of adverse events will be compared by Fisher's Exact Test. Special attention will be given to those participants who have discontinued due to adverse events or experienced a serious adverse event. Exploratory analyses such as determining if baseline blood neurosteroid or choline levels predict response and whether changes in these levels are associated with clinical response will be conducted using a mixed model (SAS Proc GLIMMIX) with baseline blood neurosteroid and choline levels as fixed effects. In addition, subgroup analyses with respect to patient demographics and characteristics may be performed as deemed appropriate by the PI and/or biostatistician. Unless otherwise noted, tests of hypotheses are 2-sided and the nominal level of significance will be 0.05.

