3.3.d. Dropouts: Retention is challenging in studies involving BPD/schizoaffective disorder and substance dependence. We have greatly improved our retention over the years by implementing 1) more frequent visits, 2) more frequent contact to remind participants of appointments, and 3) the use of a psychosocial platform. To minimize attrition, we will obtain multiple contact numbers, pay participants small sums at each visit, and to the extent possible have the same research coordinator and psychiatrist assess participants at each visit. In addition, data will be analyzed using an analysis that uses all of the available data and allows for missing data. We will also use a contingency management strategy in which participants are given small vouchers that increase in value with consecutive appointments attended and reset following a missed appointment. We included a similar strategy in a recently completed study in BPD and cocaine dependence (Dallas site) and observed substantial improvement in retention. We anticipate that, using the above approach and considering completion rates in both PI's studies, the proposed study will have a completion rate > 70%. Although we will make every effort to minimize missing visits and dropouts, dropouts and missing visits are common in longitudinal studies. Therefore, we will do comprehensive sensitivity analyses to investigate the consequences of incomplete observations in the analysis of repeated measurement data using local influence, pattern mixture models and multiple imputations.¹³⁵⁻¹³⁷

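### The 81.4% power counts every randomised participant as analysed and is tied to an observed interim effect, and the two-arm path has no power figure

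*Combined protocol and SAP*

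**What the plan says.** The trial is planned for 199 participants (Section 3.3.b). In Section 3.3.c, under Sample size re-estimation, the plan states for Stage 1 that "we will recruit 99 subjects (i.e., 33 subjects per arm) with 1:1:1 treatment allocation ratio", and then that "an additional 100 subjects at 1:1 ratio will be recruited at Stage 2". The rule for keeping both drugs is: "If both treatments have an effect size of at least 0.50 then neither treatment is dropped". For that branch the plan says "then we will have 81.4% power with 66 participants per arm and the study will continue with three treatment arms". No other power figure appears in the document.

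Three other statements bear on it:

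- **Analysis set** (Section 3.3.c, General Analytic Plan): the primary analysis uses an intention-to-treat population defined as "all randomized participants who have at least one follow-up evaluation".
- **Significance level** (Section 3.3.c, Statistical Methods): unless otherwise noted, "tests of hypotheses are 2-sided and the nominal level of significance will be 0.05". No multiplicity adjustment is described.
- **Attrition** (Section 3.3.d): the plan anticipates that "the proposed study will have a completion rate > 70" per cent, and says the analysis will use all available data.

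**The concern.** A power figure is only as good as the number analysed and the effect assumed. Here the number per arm equals total enrolment divided by three, so nothing is held back for participants who drop out of the primary analysis set. The effect is the one that would be observed at the interim analysis, when each arm has 33 participants and the estimate is imprecise. The branch that the plan describes as its default for Stage 2, one drug against placebo, has no power figure at all.

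The DSMB and the funder's programme official will use this section to decide which arms continue. The only power statement they have is slightly too favourable for its own branch, is conditioned on the wrong quantity, and does not cover the other branch.

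**Working it through.** **Inputs**

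- Randomised: 199 in total; 33 per arm in Stage 1; 100 more in Stage 2 (Sections 3.3.b and 3.3.c).
- Effect size 0.50; two-sided 5% level per test (Section 3.3.c).
- Share with at least one post-baseline visit (Section 3.3.a): pilot study 2, (60 + 61)/130 = 93.1%; pilot study 4, 73/80 = 91.3%. Applying these shares here is an assumption. Those pilots studied bipolar disorder with cocaine dependence and bipolar depression.

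**Formula.** For n analysed per arm and true standardised effect d, the two-sample t-test has 2n − 2 degrees of freedom and noncentrality d × √(n/2). Power is the probability that this noncentral t falls outside the two-sided critical values.

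**1. The plan's figure.** With n = 66 and d = 0.50, the noncentrality is 0.50 × √33 = 2.872 on 130 degrees of freedom, and power is 81.35%. This rounds to the stated 81.4%.

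**2. Where 66 comes from.** 199/3 = 66.3. This is the number randomised, with no deduction.

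**3. Power at the analysed number, three arms, d = 0.50, unadjusted**

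- 66 × 0.931 = 61.4, so 61 analysed: 78.2%.
- 66 × 0.9125 = 60.2, so 60 analysed: 77.5%.

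Eighty per cent power needs 64 analysed per arm. At these shares that is 64/0.931, rounded up to 69 randomised, or 64/0.9125, rounded up to 71.

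**4. Precision of the interim effect.** With 33 per arm the standard error of the standardised difference is about √(2/33) = 0.246. An observed 0.50 therefore has an approximate 95% interval of 0.50 ± 1.96 × 0.246, or 0.02 to 0.98. Observing 0.50 does not establish a true effect of 0.50.

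**5. The two-arm path.** Randomised per arm: 33 + 50 = 83. Analysed at 93.1%: 83 × 0.931 = 77.

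| True d | 83 analysed | 77 analysed |
|---|---|---|
| 0.50 | 89.3% | 86.9% |
| 0.40 | 72.6% | 69.4% |
| 0.25 | 36.0% | 33.8% |

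These are unadjusted and ignore the selection of the better drug at the interim analysis.

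**6. Two comparisons.** Two unadjusted 5% tests sharing a placebo arm (correlation 0.5) have a familywise error of 1 − P(both |Z| < 1.96) = 9.1%, treated as a fixed design. A Dunnett adjustment (critical value 2.21, per-test level 0.0270) would give 73.7% per comparison with 66 analysed, 69.9% with 61 and 69.1% with 60.

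**7. Power conditional on the interim rule.** I simulated both stages with a normal approximation, a shared placebo arm, 60 to 66 analysed per arm, and Stage 1 data carried into the final test. If both drugs truly have d = 0.50, both reach 0.50 at the interim in about 33% of trials and the two-arm path is taken in about 61% (with 33 per arm analysed at the interim). Given entry to the three-arm path, success per comparison (unadjusted) is about 96% to 97% at true d = 0.50 and about 75% to 79% at true d = 0.25.

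**The case against.** The best defence is that the number is correct for what it calculates, and that several ways of attacking it go too far. Much of this stands.

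- **Not an arithmetic error.** The stated figure reproduces to the decimal. The weakness lies in its inputs.
- **Two comparisons do not reduce the planned power.** A reader might infer that testing two drugs cuts the 81.4%. The plan tests each at a nominal 5% with no adjustment, so each test keeps its power. What rises is the familywise error, to about 9%. The Dunnett figures apply only if the sponsor adopts that rule.
- **Non-completion is not loss from the analysis.** A reader might take the expected completion rate and conclude that only 46 per arm (70% of 66) contribute, for a power of 66.0%. The documents do not support that: visits are weekly, one follow-up evaluation is enough to enter the primary set, and all available data are used. The supportable loss is 3 to 4 percentage points.
- **The three-arm path is not a 70% path.** A reader might label the adjusted figure as that branch's power. Entry requires both interim effects to reach 0.50 and those data are reused, so conditional success is much higher at a true 0.50. It also differs from 81.4%, which is therefore not conditional power either.
- **Partial safeguards exist.** The DSMB may recommend sample size re-estimation, and a predictive confidence interval is planned at the interim analysis. Neither is tied to loss from the analysis set, and neither supplies a power figure for the two-arm path.

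The defence does not answer three points: 66 is the randomised number, power is made to follow from an observed effect, and the two-arm path has no figure.

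**Conclusion.** The concern holds, at modest size. As fixed-design power per comparison at a true effect of 0.50, the figure is about 77.5% to 78.2% on the analysed numbers suggested by the plan's own pilots, against 81.4% stated. The wording that derives power from the observed interim effect is wrong in principle, whatever the number. The missing two-arm figure is the larger practical gap. At a true 0.25, which is the size the interim rule treats as clinically meaningful, two-arm power is only about 34% with 77 analysed.

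This rests on a 91% to 93% share with follow-up, carried over from other populations, and on equal loss across arms. It also uses a two-sample formula, whereas the planned analysis is a repeated-measures GEE. Power under the GEE may differ in either direction, and the documents give no within-person correlation with which to calculate it. Participants who leave early also contribute fewer visits, and that loss cannot be priced for the same reason.

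**What to change.** Replace the 81.4% sentence in Section 3.3.c with a short statement of fixed-design power per comparison for each path, giving the true effect assumed and the number expected in the primary analysis set:

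- **Three arms:** about 78% at a true effect size of 0.50, with 60 to 61 analysed of 66 randomised per arm, unadjusted. State the multiplicity choice: either a Dunnett adjustment, which gives about 69% to 70%, or no adjustment with a familywise error of about 9%.
- **Two arms:** about 87% at 0.50, 69% at 0.40 and 34% at 0.25, with about 77 analysed of 83 randomised per arm, before any adjustment for selecting the better drug.

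Label these as fixed-design figures and say that they are not conditional on passing the interim rule. Delete the wording that makes power follow from the observed interim effect. State the assumed share with follow-up and its source, so that it can be checked at the interim analysis.

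The cost is a change of text and a less favourable stated figure. It needs no extra participants and no change to the design.

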Adaptive Clinical Trial Designs: As reviewed above, the BPD/schizoaffective disorder and alcohol use disorder combination is challenging to treat. A study design that facilitates development of better treatment approaches would be highly beneficial. The FDA Critical Path Initiative called on industry and researchers to develop innovative adaptive methods for making clinical trials more efficient and thereby less costly and timeconsuming.¹⁰⁴ Adaptive designs can answer the same questions as traditional efficacy trials but with notable advantages in flexibility and efficiency (e.g. fewer participants) without loss of scientific rigor or credibility.¹⁰⁵ Adaptive clinical trial designs are of much interest in many fields of medicine including drug abuse,¹⁰⁶ respiratory diseases, oncology, and stroke.¹⁰⁷ Adaptive trial designs permit critical mid-trial design modifications, based on interim information, without undermining the validity and integrity of the trial. The proposed study lends itself to an adaptive drop-the-loser (DTL) design that permits evaluation of a range of treatment arms for evidence of clinical effect. As compared to standard design, DTL provides for a decrease in expected treatment failures, while preserving the power of the study, and decreasing the number of people exposed to placebo.¹⁰⁸ Thus, the design is potentially safer, faster, less expensive and more efficient than traditional designs. Using this design, both treatments in the proposed study will be compared to placebo using a three-arm, randomized, double-blind design. An interim analysis plan, conducted after 50% of participants have been enrolled, will apply predetermined decision rules for dropping a treatment condition that fails to show clinically meaningful efficacy over placebo. This adaptive "pruning" permits randomization of remaining participants to a condition that demonstrates the most encouraging performance. Thus, the proposed design allows for assessment of multiple medications, as well as an adequately powered trial of the most promising one, in a single trial, an approach that is efficient both in time and resources. In addition, this design is consistent with an objective of the NIAAA PA the application is in response to, which highlights development and implementation of adaptive clinical trial designs in alcoholism clinical research.

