3.2. Innovation

Alcohol dependence is very common in BPD and schizoaffective disorder. However, literature on the treatment of these dual-diagnosis populations is quite limited. Thus, the patient population studied is innovative. The drugs tested are also innovative. Each is a dietary supplement with interesting clinical and preclinical properties. In addition, the two treatment options have different mechanisms of action that are relevant to alcohol use disorders and BPD/schizoaffective disorder but have not been the focus of extensive attention. Thus, the proposal is consistent with the NIAAA goal to "Discover, develop, and test new, more effective agents to prevent or reduce drinking" (NOT-AA-14-008). The 2-site clinical adaptive trial design is innovative. Adaptive designs are widely used in some areas of medicine, and are currently being explored in the drug abuse field,¹⁰⁶ but, to our knowledge, have not been used in alcohol research. The design allows for the testing of two treatments as well as an adequately powered trial of the more promising option. The stopping rules are also innovative. If neither of the treatments appears promising, the trial will be stopped. This approach decreases the investment of time and resources should the treatments appear to not be very

effective. If an option is promising then the timeframe for drug development will be faster than with current approaches. We suggest that this approach is consistent with the objective of NIAAA to conduct more efficient clinical trials with novel methodology,¹⁰⁹ and with the specific PA. *Finally, we include an exploratory analysis that will examine, with both medications, whether changes in alcohol use occur before or after changes in alcohol craving, mood or cognition. To our knowledge, such an analysis has not been reported in dual BPD/schizoaffective disorder and alcohol use clinical trials. The findings will help inform whether the effects of the medications on alcohol use are driven by improvement in craving and other clinical outcomes.*

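### The statistical reason for continuing at an interim effect size of 0.25 assumes growth that enrolment cannot produce; the two-arm trial has 36% power at 0.25 and 89% at 0.50

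*Combined protocol and SAP*

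**What the plan says.** Section 3.3.c stops the trial at the interim if both drugs show effects "smaller than a minimum clinically important difference, defined as an effect size of 0.25". If one drug reaches 0.25, the trial continues as that drug against placebo.

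Under the sample size heading, the section gives two reasons for 0.25. One is clinical: a new drug should do better than the 0.15-0.20 it reports for naltrexone. The other is statistical: an interim value of 0.25 "provides a reasonable likelihood of a significant difference from placebo at study completion assuming some increase in effect size as more participants are" recruited. The sentence puts this growth down to more people being "enrolled and the variance of the data decreases".

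The same paragraph says that the 33 per arm of Stage 1 give a clinically meaningful minimum "effect size of 0.25 between each treatment arm and placebo with" a two-sided 5% test. The only power in the plan is for the three-arm continuation: if the effect for both drugs "is at least 0.50 at interim analysis then we will have 81.4% power with 66 participants per arm".

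For the two-arm continuation, the adaptive-design paragraph of Section 3.1 promises an assessment of several drugs "as well as an adequately powered trial of the most promising one". Section 3.2 repeats this: "as well as an adequately powered trial of the more promising option". Neither section, nor 3.3.c, gives a power, an assumed effect or a per-arm total for that trial.

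**The concern.** A standardised effect size is a mean difference divided by the population SD. Recruiting more people from the same population makes the estimate more precise, but moves neither the difference nor the SD in any expected direction. The plan therefore supports its continuation threshold with a property that the design does not have. A DSMB or funder told that 0.25 carries a reasonable chance of final success, because the effect should grow, would be working from too favourable a picture.

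The two-arm trial is the form in which the plan describes Stage 2 when one drug is retained, yet its reader is told only that it is adequately powered. Whether that is so depends on the effect assumed, and the plan's own minimum clinically important difference is an obvious effect to test it at.

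**Working it through.** **Inputs (Section 3.3.c).** Two-sided 5% level. Stage 1: 33 per arm. Stage 2: 100 more at 1:1, so 50 per arm. Both stages are pooled, so the two-arm path ends with 33 + 50 = 83 per arm. Interim cut-off: 0.25. Stated power: 81.4% at 0.50 with 66 per arm. Assumed: comparison of two means, SD scaled to 1, everyone analysed, no re-estimation.

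**1. Reproduce the plan's figure.** Two-sample t-test, df = 2n − 2, noncentrality d√(n/2). For n = 66 and d = 0.50 the noncentrality is 0.50 × √33 = 2.87 and power is 81.35%, which matches 81.4%. This identifies the method.

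**2. What enrolment changes.** The standard error of the standardised difference is √(2/n): 0.246 at 33 per arm and 0.155 at 83. The SD and the true effect δ do not depend on n. Starting from an interim value of 0.25, the expected final estimate is (33 × 0.25 + 50δ)/83:
- δ = 0: 8.25/83 = 0.10
- δ = 0.25: 20.75/83 = 0.25
- δ = 0.50: 33.25/83 = 0.40

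A rise is expected only if the true effect already exceeds 0.25. Enrolment does not create it.

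**3. If the estimate stays at 0.25.** t = 0.25/0.155 = 1.61 on 164 df, so p = 0.11. The smallest final estimate with p < 0.05 is about 0.307 (0.304 by the normal approximation).

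**4. Conditional power from exactly 0.25.** Stage 2 alone must show (1.96 × √(2/83) × 83 − 0.25 × 33)/50 = (25.25 − 8.25)/50 = 0.340. Its standard error is √(2/50) = 0.20. The chance of final significance is 1 − Φ((0.340 − δ)/0.20):

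| True effect | z needed | Chance |
|---|---|---|
| 0 | 1.70 | 4% |
| 0.25 | 0.45 | 33% |
| 0.50 | −0.80 | 79% |

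**5. Stage 1 alone.** With n = 33 and d = 0.25, power is 17%. The smallest observed effect with p < 0.05 is 0.49. So 33 per arm do not deliver a 5% test of 0.25; the figure can work only as a stop/continue cut-off.

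**6. Two-arm path, 83 per arm, method of step 1.**

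| True effect | Power |
|---|---|
| 0.25 | 36.0% |
| 0.40 | 72.6% |
| about 0.44 | 80% |
| 0.50 | 89.3% |

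**The case against.** The strongest reply is that nothing numerical in the plan is wrong. The one stated power reproduces, 0.25 is a stopping threshold for which no power is claimed, and it has a clinical rationale of its own. At 0.50, the only effect at which the plan quotes power, the two-arm trial does better (89%) than the three-arm trial (81.4%). All of that stands. Had the two-arm power merely been left out, this would be a request for detail. It is a correction because a stated premise is false and the Stage 1 sentence does not hold as written.

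Sample size re-estimation may also be said to cover the gap. Section 3.3.c says in one place that it will be done and in another that it may be, and it mentions a desired power without a number. No target, rule or cap is given, and blinded re-estimation cannot respond to a small effect. It does not supply the missing figure.

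The planned GEE uses repeated visits and may be more efficient. If the effect size is on a single-visit SD and 12 weekly visits are averaged at an assumed correlation of 0.5 to 0.9, 17%, 36% and 89% become 18-27%, 39-59% and 92-99%. The plan's 81.4% takes no such gain.

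A reader might infer that the retained drug's estimate will generally fall after the interim. The documents do not support that as a rule. From exactly 0.25 the estimate rises with probability 50% if the true effect is 0.25 and 89% if it is 0.50. Across all two-arm continuations the answer depends on the true effects and on which continuation rule applies, and the section does not settle the latter. In simulation the mean went from 0.44 to 0.31 with true effects of 0.25 and 0. It rose from 0.45 to 0.48 with both at 0.50, if three arms continue whenever both drugs reach 0.25.

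**Conclusion.** The point holds for the stated rationale and for two descriptions. The growth clause is wrong, and at the cut-off the chance of final significance is about one in three if the true effect is 0.25. The 33 per arm of Stage 1 cannot test 0.25 at the 5% level (power 17%). The two-arm trial is fairly called adequately powered at 0.50, but not at the plan's own minimum clinically important difference (36%); the description fits effects of about 0.44 or more.

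These are simple two-sample figures on the same basis as the 81.4%, without dropout, re-estimation or any repeated-measures gain. The primary population is "defined as all randomized participants who have at least one follow-up evaluation", so participants with no follow-up would lower them.

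Two stronger readings should be resisted. The trial was not designed for 36% power: the documents use 0.25 as a threshold and never as a powering target. Nor can one overall two-stage success probability be quoted, because it depends on the assumed effect of the second drug. With both drugs effective at 0.25 or at 0.50, at least one is confirmed in 40% or 90% of simulated trials, and the figures are lower if one is inert. The final test itself is not put in doubt by this point.

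**What to change.** Change the text of Section 3.3.c only; the cut-off, sample size and decision rule stay as they are.

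(a) Delete the clause on growing effect size and falling variance, and keep the clinical reason. In its place state that, from an interim effect of exactly 0.25 with 50 more per arm, the chance of final significance is about 4%, 33% and 79% for true effects of 0, 0.25 and 0.50.

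(b) Reword the Stage 1 sentence so that 0.25 is a stop/continue cut-off, not an effect that 33 per arm can test at the 5% level.

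(c) State the two-arm power at 83 per arm: 36% at 0.25, 80% at about 0.44, 89% at 0.50. Tie the adequately-powered wording in Sections 3.1 and 3.2 to effects of about 0.44 or more. Note that these are two-sample figures without dropout, re-estimation or repeated-measures gain. Keep the 81.4%.

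The cost is one reworded paragraph and a qualifier in two others. The stated chance of success will look less favourable near 0.25.
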